## 10.2 Derived and Transformed Data

For ECGs, vital signs, glucose, insulin, glucagon, cortisol and neurological examinations recorded on Day -1 the baseline will be the -24 h value and for Day 0 the baseline will be the pre-dose value on Day 0. The  $AUC_{0-24}$  for change from baseline in glucose, insulin, glucagon and cortisol will be calculated on Day -1 and Day 0, using the linear-linear trapezoidal method. For prolactin and leptin the baseline will be pre-dose on Day 0.

Laboratory data will be reported in standard units. The baseline will be the latest value recorded pre-dosing on Day 0. Out-of-range laboratory tests may be repeated. If a test is out-of-range at a baseline timepoint and repeated before dosing, the latest repeat value before dosing will be used as baseline. However, if a test is out-of-range and repeated at any other time during the study, the out-of-range value (not the repeat value) will be included in statistical summaries.

Triplicate ECG measurements will be made at some timepoints on Day -1 and Day 0, the mean of the three measurements for each subject will be used at each timepoint.

The pharmacokinetic parameters to be derived are given in Appendix B

## 10.3 Assessment Windows

No assessment windows are defined for this report.

## 10.4 Values of Potential Clinical Importance

Any laboratory value outside the reference interval for that variable will be flagged with an 'H' if it is higher than the reference interval, and with an 'L' if it is lower. Additionally, if, during the course of the trial, a variable changes from baseline (Day 0) by more than a predetermined amount (as defined by the Principal Investigator, Appendix A), that value will receive a flag 'I' if increased, or 'D' if decreased. Therefore, if a value both falls outside the reference interval and alters from the baseline value by more than the predetermined amount, it will attract a double flag and will be considered to be potentially clinically important.

A vital signs result will be considered to be of potential clinical importance if it falls outside the relevant range below:

Vital Sign	Range
Supine/semi-recumbent systolic blood pressure	85–160 mm Hg
Supine/semi-recumbent diastolic blood pressure	40–90 mm Hg
Supine/semi-recumbent heart rate	40–100 beats/min
Respiration rate	8–20 per min
Oral temperature	35.5–37.8°C

QTcB or QTcF > 450 msec and increases in QTcB or QTcF from baseline of > 30 msec will be considered to be potentially clinically important.

## **11 Study Population**

### **11.1 Disposition of Subjects**

The disposition of all subjects in the safety population will be summarised including: number of subjects randomised; number completing the study (i.e. not withdrawn), by treatment; and number discontinued (withdrawn) from the study. The number of subjects in each analysis population will be summarised by treatment.

All subjects who withdraw or are withdrawn from the study will be listed, by treatment, with the reason for withdrawal.

A listing of analysis populations will be provided.

### **11.2 Protocol Deviations**

Before closing the database, data listings will be reviewed to identify any significant deviations and determine whether the data should be excluded from any analysis populations.

Major protocol deviations include subjects who:

- Entered the study even though they did not satisfy the entry criteria.
- Met the criteria for withdrawal from the study but were not withdrawn.
- Received the wrong treatment or incorrect dose.
- Received an excluded concomitant therapy.
- Received investigational product(s) past the expiration date and time.

- Had their treatment assignment unblinded.

In addition, subjects with minor time deviations (measurements taken outside the allowable windows given in the protocol) will be identified.

### **11.3 Demographic and Baseline Characteristics**

Demographic and baseline characteristics (e.g. physical examination, neurological examination, vital signs and ECGs) will be listed and summarised.

Subjects who take concomitant medication will be listed. All non-trial medication will be coded using version September 2016 of the WHO Drug dictionary.

### **11.4 Treatment Compliance**

Dates and times of dosing will be listed.

## **12 Safety Analyses**

Summaries and listings of safety data will use the safety population.

### **12.1 Extent of Exposure**

The dates and times of treatment dosing will be listed to indicate exposure to the study medication.

### **12.2 Adverse Events**

Adverse events will be coded using the version of the Medical Dictionary for Regulatory Activities (MedDRA) (version 20.0).

All adverse events will be listed.

The number of subjects with at least one treatment-emergent adverse event (TEAE) will be tabulated by actual treatment and MedDRA system organ class and preferred term. A treatment-emergent adverse event is defined as an event emerging during treatment having been absent pre-treatment or having worsened relative to pre-treatment.

For each of the following, the number of subjects with adverse events will be summarised by actual treatment:

- TEAEs by system organ class and preferred term
- Drug-related (“related” as recorded by the Investigator) TEAEs by system organ class and preferred term

Subjects with more than one TEAE will be counted only once, at the greatest severity or causal relationship, for each system organ class and preferred term. Adverse events with missing severity and/or causality will be treated as severe and related, respectively.

Summaries will be sorted by system organ class and decreasing total incidence of preferred term.

### **12.3 Deaths and Serious Adverse Events**

Adverse events leading to deaths and serious adverse events will be listed separately (fatal events will be listed separately from non-fatal events).

### **12.4 Adverse Events Leading to Withdrawal from the Study**

Adverse events leading to withdrawal will be listed separately.

### **12.5 Clinical Laboratory Evaluations**

Haematology, clinical chemistry and urinalysis evaluation at each planned assessment, and change from baseline at each planned post-baseline assessment, will be summarised by actual treatment.

Urinalysis parameters will also be listed.

All laboratory values of potential clinical importance will be listed and all related laboratory results (i.e. haematology or clinical chemistry) for subjects with values of potential clinical importance will be listed, separately. Frequencies of laboratory values of potential clinical importance will be summarised.

## **12.6 Other Safety Measures**

### **12.6.1 Vital signs**

Vital signs evaluation at each planned assessment, and change in vital signs baseline at each planned post-baseline assessment, will be summarised by actual treatment. Individual subject profiles will be plotted for each vital sign parameter (Blood Pressure and Heart Rate).

Vital signs data of potential clinical importance will be listed separately.

### **12.6.2 ECG**

QT interval data will be presented using Bazett's (QTcB) and Fridericia's (QTcF) corrections. ECG data will be summarised by treatment and time point. Differences from baseline will be summarised by treatment and time point.

The number of subjects with a potentially clinically important ECG value will be summarised by actual treatment and time point, giving the numbers of subjects with QT, QTcB or QTcF > 450 msec, > 480 msec and > 500 msec, and the numbers of subjects with increases in QT, QTcB or QTcF from baseline of > 30 msec and > 60 msec. A supporting listing of all subjects with an ECG value of potential clinical importance and a separate listing of ECG findings classified as abnormal by the Investigator will also be provided.

### **12.6.3 Neurological examination**

Neurological examination results will be summarised and normal and abnormal neurological examination findings will be listed in detail according to the CRF. Total scores from neurological questionnaires at each planned assessment, and change from baseline at each planned post-baseline assessment, will be summarised by actual treatment.

Total scores from neurological questionnaires will also be listed.

### **12.6.4 Physical examination**

Physical examination results will be summarised and abnormal physical examination findings will be listed.

### **12.6.5 Ophthalmology assessments**

Ophthalmology assessments results will be summarised and listed by time point.

## 13 Pharmacokinetic Analyses

Analytical Services International Ltd, London, U.K. will measure the plasma and urine concentrations of emodepside. The pharmacokinetic analysis will be done by Statistics and Data Management Department at HMR. Pharmacokinetic parameters will be calculated using WinNonlin, version 6.3.

In addition, the plasma and urine concentration of emodepside metabolite(s) may be measured. If and when these data become available a SAP amendment will be written to specify their reporting (if applicable).

The pharmacokinetic parameters to be derived are given in Appendix B.

PK concentration data will be summarised using the PK concentration population. PK parameters will be summarised using the PK Parameter population.

For log transformed parameters, the primary measure of central tendency will be the geometric mean; for untransformed parameters, it will be the arithmetic mean or median.

For all variables N (number of subjects receiving the treatment/formulation in the population), n (number of observations), arithmetic mean, median, minimum, maximum, SD, %CV, and the 95% confidence interval for the arithmetic mean will be provided. For log-transformed variables, all of the above plus the geometric mean, which is the anti-logged arithmetic mean of log-transformed variables, its 95% confidence interval and the SD of the logs will be provided.

The between-subject CV will be calculated using:

1.  $\%CV_b = 100 * (SD/Mean)$  with SD and Mean of untransformed data
2.  $\%CV_b = 100 * \sqrt{(\exp(SD)^2 - 1)}$  with SD of log-transformed data

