**Template T\_PK4**

Table 14..2.xx Summary of Log-Transformed Derived Emodepside Plasma Pharmacokinetic Parameters

Parameter	Treatment	N	n	Geom Mean	95% CI	SD (logs)	{%CVb}
AUC last (units)							
C max (units)							

Source: Listing 16.2.xx

*Programming notes:* Continued with all dose levels and parameters

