## **2 General Considerations for Data Analysis**

### **2.1 Derived and transformed data**

In general, concentration and concentration-related quantities, rate constants and half-lives (e.g.  $C_{\max}$ , AUC,  $t_{1/2}$ , CL/F,  $V_z/F$  and MRT) will be analysed after logarithmic transformation. Logarithmic transformations will use natural logarithms ( $\log_e$ ). A list of those parameters that will be log transformed are given below.

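### The SAP's CV formula for log-transformed PK data squares exp(SD) instead of SD, so the geometric CV would be overstated at any log SD below 2

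*SAP*

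**What the plan says.** SAP section 13 gives two formulas for the between-subject CV. The first, for untransformed data, is the SD divided by the mean, times 100. The second is "CV_b = 100 * \sqrt{(\exp(SD)^2 - 1" (the closing brackets fall outside the quote), to be used "with SD of log-transformed data". The SAP appears twice in the document set, and both copies place the exponent outside exp().

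Appendix B 2.1 settles the log base: "Logarithmic transformations will use natural logarithms". It applies the log transformation to concentration-related quantities and also to "rate constants and half-lives". The parameter table in Appendix B 3.1.1 marks 17 parameters for log transformation, including Cmax, AUC∞, AUC0-24 and their dose-normalised forms.

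The result goes to Table 14.2.1.3, template T_PK4, titled "Summary of Log-Transformed Derived Emodepside Plasma Pharmacokinetic Parameters". There {%CVb} is printed beside the geometric mean, its 95% CI and the SD of the logs. Protocol section 10.5 asks for %CV and the SD of the logged variables but gives no formula. SAP section 15, which lists changes from the protocol, does not mention the CV.

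**The concern.** Once natural logarithms are specified, the CV of a log-normal variable is fixed by an identity and is not a matter of convention. The printed expression is a different function of SD.

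A program that followed the text would report between-subject variability that is far too high for every parameter in Table 14.2.1.3. Table 14.2.1.2 (template T_PK3) reports the arithmetic %CV for the same parameters, so the study report would carry two sharply different CVs for the same data without explanation.

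Protocol section 3.3 says the data from this study will inform the design of later Phase I studies. Between-subject CV is a common input to such designs, and a reader who took the printed value at face value could be misled.

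**Working it through.** **Inputs**
- Formula as written: SAP section 13, formula 2.
- SD: that of the log-transformed data (same place).
- Log base: natural (SAP Appendix B 2.1).
- Log SD values: none are given in either document, so the range below is assumed. There is no CV in the plan to reproduce.

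**The two forms.** If ln X is normal with standard deviation s, then

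- log-normal CV: 100·sqrt(exp(s²) − 1)
- as written: 100·sqrt([exp(s)]² − 1) = 100·sqrt(exp(2s) − 1)

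They are equal when s² = 2s, that is at s = 2 (or trivially at s = 0). For 0 < s < 2 we have 2s > s², so the written form is too high. For s > 2 it is too low.

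**One case in full, s = 0.3**
- Log-normal CV: s² = 0.09; exp(0.09) = 1.0942; minus 1 = 0.0942; square root = 0.307, so 30.7%.
- As written: exp(0.3) = 1.3499; squared = 1.8221; minus 1 = 0.8221; square root = 0.907, so 90.7%.
- Ratio: 2.95.

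**Range of assumed log SDs**

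| Log SD | Correct CV (%) | As written (%) | Written / correct |
|---|---|---|---|
| 0.1 | 10.0 | 47.1 | 4.69 |
| 0.2 | 20.2 | 70.1 | 3.47 |
| 0.3 | 30.7 | 90.7 | 2.95 |
| 0.4 | 41.7 | 110.7 | 2.66 |
| 0.5 | 53.3 | 131.1 | 2.46 |
| 0.7 | 79.5 | 174.8 | 2.20 |
| 1.0 | 131.1 | 252.8 | 1.93 |
| 1.5 | 291.3 | 436.9 | 1.50 |
| 2.0 | 732.1 | 732.1 | 1.00 |
| 2.5 | 2273.8 | 1214.1 | 0.53 |

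**Two checks on the correct form**
- Simulation of 4,000,000 log-normal values gave a CV of 20.2% at log SD 0.2 and 53.3% at 0.5, matching the second column.
- For small s the CV must approach s itself. At s = 0.05 the log-normal form gives 5.0%. The written form gives sqrt(exp(0.10) − 1) = 32.4%, so it cannot be an alternative definition of the CV.

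**What is not touched.** Geometric means and their CIs, the SD of the logs, the arithmetic %CV (formula 1) and the food-effect 90% CI in SAP section 13.1.2 do not use formula 2.

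**The case against.** The strongest reply is that this is loose notation: the author may have meant exp applied to (SD)², and the programmer may well have used the right form. That is possible, and nothing in the documents shows how the program was written. But the usual reading of the printed expression squares the exponential, both copies of the SAP show it that way, and no other section gives a correct version. SAP section 3 also says that departures from the SAP will be documented in the trial report. A program with the right formula therefore departs from the text, and a program that follows the text prints wrong values.

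A second reply is that the column may never be produced. The braces around {%CVb} resemble the placeholder braces used elsewhere in the templates, and the list of log-scale statistics in section 13 does not name a geometric CV. Against this, section 13 states without condition that the between-subject CV is to be calculated by the two formulas. The braces leave some doubt about the display but do not remove the instruction.

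The remaining replies concern weight, and they stand:
- This SAP covers only Part 2, which is two exploratory cohorts with six subjects planned on active drug in each. Part 1 is reported separately.
- The protocol does not say that CVs from this table will set any later sample size.
- A CV of 91% beside an arithmetic CV near 31% would probably be noticed, and the correct value can be recovered from the adjacent SD of the logs.

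These points limit the consequence; they do not make the formula right.

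**Conclusion.** The concern holds. Given natural logarithms, formula 2 in SAP section 13 is not the CV of log-normal data. It overstates that CV at every log SD between 0 and 2. The overstatement is about 3.5-fold at an assumed log SD of 0.2 and about 2.5-fold at 0.5.

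The algebra is certain. The size depends on two assumptions: the log SD, which the documents do not give, and literal programming of the text. The effect is limited to one descriptive column in one table. No safety conclusion, geometric mean or confidence interval depends on it. It should still be corrected, because a stated rule that gives a wrong number when followed should not remain in the SAP.

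**What to change.** In SAP section 13, replace formula 2 with %CVb = 100·sqrt(exp(SD²) − 1), where SD is the standard deviation of the natural-log data. Then confirm that the Part 2 SAS program for Table 14.2.1.3 uses that form, and correct it if it does not.

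The cost is one exponent moved in the text and one program check. No other output needs to be rerun.

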### 13.1 Plasma PK

#### 13.1.1 Pharmacokinetic Concentration Data

The plasma concentrations of emodepside and metabolites (if applicable) will be listed and summarised by treatment. Means at any time will only be calculated if at least 2/3rds of the individual data points are above the lower limit of quantification.

Individual and mean plasma concentration–time profiles will be presented graphically.

### **13.1.2 Pharmacokinetic Parameters**

The pharmacokinetic parameters of emodespide and metabolites (if applicable) will be listed and summarised by treatment.

To assess the effect of food, analysis of variance (ANOVA) models will be fitted to the fed (Part 2, Cohort 9) solution and relevant fasted (Part 1, Cohort 5) solution data with the logarithm of the pharmacokinetic parameters  $AUC_{0-24}$  as the dependent variable, and formulation as a fixed effect. The estimated least square means and residual variance from the model will be used to construct 90% CIs for the difference in means on the log scale for the comparison of fed versus fasted solutions.

### **13.2 Urinary PK**

If concentrations of emodespide in urine are determined, the amount of emodespide excreted in the urine will be estimated. The data will be listed and summarised by treatment.

## **14 Pharmacodynamic Analyses**

Summaries and listings will use the safety population.

Pharmacodynamic variables (glucose, insulin, glucagon, cortisol, prolactin and leptin) at each planned assessment, and change from baseline at each planned post-baseline assessment, will be summarised by actual treatment.

In addition, for glucose and insulin (Cohorts 9 and 10), glucagon and cortisol (Cohort 9):

- Individual subject profiles will be plotted
- The difference between change from baseline on Day 0 and Day -1 will be summarised at each planned post-baseline assessment by actual treatment
- The  $AUC_{0-24}$  of change from baseline will be summarised for each day and treatment

Individual Insulin and PK Concentration Plots, including Related Significantly Important AE Durations will be produced.

For calculation of pharmacodynamics parameters, summary statistics and individual profile plots, values below the quantifiable limit of the assay will be substituted by one half of the lower limit of quantification.

## 15 Changes from the Protocol Specified Statistical Analysis

After the study was submitted to the MHRA and ethics committee the following changes were made to the analyses:

- 1) The definition of treatment-emergent adverse event has been updated from “an AE will be considered as treatment emergent if it appeared after the first dosing, or if appeared before dosing and worsened after dosing” to:

A treatment-emergent adverse event is defined as an event emerging during treatment having been absent pre-treatment or having worsened relative to pre-treatment.

- 2) The  $AUC_{0-24}$  of change from baseline for glucose, insulin, glucagon and cortisol will be summarised for each day and treatment

- 3) The following emodepside parameters have been added to those mentioned in the protocol:

Main PK parameters:  $AUC_{0-24}$  and  $AUC_{0-24}/D$

Exploratory PK parameters:  $AUC_{0-24, norm}$ ,  $t_{1/2, dom}$

- 4) The following analyses have been added for glucose, insulin, glucagon and cortisol:

The difference between change from baseline on Day 0 and Day -1 will be summarised at each planned post-baseline assessment by actual treatment

The  $AUC_{0-24}$  of change from baseline will be summarised for each day and treatment

## 17 ATTACHMENTS

### 17.1 Table of Contents for Data Display Specifications

For overall page layout refer to [Appendix C](#).

Tables, figures and listings will be labelled B for Part 2, e.g., 14.1B

The numbering in the tables below will take precedence over the numbering in the shells.

CONFIDENTIAL

The following tables and figures will be produced (templates provided in Sections 17.2.1 and 17.2.2):

Table	Description	Population	Source Listing	Template (Shells below)
10.1	Summary of Subject Disposition	Safety	16.2.1.2, 16.2.3.1	T_SD1
14.1	DEMOGRAPHIC DATA			
14.1	Summary of Demographic Characteristics	Safety	16.2.4.1	T_DM1
14.2	PHARMACOKINETIC AND PHARMACODYNAMIC DATA			
14.2.1.1	Summary of Emodepside Plasma Pharmacokinetic Concentration-Time Data (ng/mL)	PK	16.2.6.1.1	T_PK1
14.2.1.2	Summary of Derived Emodepside Plasma Pharmacokinetic Parameters	PK	16.2.6.1.2	T_PK3
14.2.1.3	Summary of Log-Transformed Derived Emodepside Plasma Pharmacokinetic Parameters	PK	16.2.6.1.2	T_PK4
14.2.1.4	Assessment of the Effect of Food on the PK of Emodepside	PK	16.2.6.1.2	T_PK7
14.2.2	Summary of Derived Emodepside Urine Pharmacokinetic Parameters	PK	16.2.6.2	T_PK3
14.2.3.1	Summary of Glucose	Safety	16.2.6.3	T_PD1
14.2.3.2	Summary of Difference Between Day -1 and Day 0 in Glucose	Safety	16.2.6.3	T_PD2
14.2.3.3	Summary of AUC 0-24 for Change from Baseline in Glucose	Safety	16.2.6.4	T_PD3
14.2.4.1	Summary of Insulin	Safety	16.2.6.3	T_PD1
14.2.4.2	Summary of Difference Between Day -1 and Day 0 in Insulin	Safety	16.2.6.3	T_PD2
14.2.4.3	Summary of AUC 0-24 for Change from Baseline in Insulin	Safety	16.2.6.3	T_PD3
14.2.5.1	Summary of Glucagon	Safety	16.2.6.3	T_PD1
14.2.5.2	Summary of Difference Between Day -1 and Day 0 in Glucagon	Safety	16.2.6.3	T_PD2
14.2.5.3	Summary of AUC 0-24 for Change from Baseline in Glucagon	Safety	16.2.6.3	T_PD3

Table	Description	Population	Source Listing	Template (Shells below)
14.2.6.1	Summary of Cortisol	Safety	16.2.6.3	T_PD1
14.2.6.2	Summary of Difference Between Day -1 and Day 0 in Cortisol	Safety	16.2.6.3	T_PD2
14.2.6.3	Summary of AUC 0-24 for Change from Baseline in Cortisol	Safety	16.2.6.3	T_PD3
14.2.7	Summary of Prolactin	Safety	16.2.6.3	T_PD1
14.2.8	Summary of Leptin	Safety	16.2.6.3	T_PD1
14.3	SAFETY DATA			
14.3.1.1	Summary of Treatment-Emergent Adverse Events	Safety	16.2.7.1	T_AE1
14.3.1.2	Summary of Drug-Related Treatment-Emergent Adverse Events	Safety	16.2.7.1	T_AE1
14.3.1.3	Summary of Treatment-Emergent Adverse Events by Severity Grade	Safety	16.2.7.1	T_AE1
14.3.1.4	Summary of Drug Related Treatment-Emergent Adverse Events by Severity Grade	Safety	16.2.7.1	T_AE1
14.3.2.1	Listing of Fatal Adverse Events	Safety	16.2.7.1	L_AE1_PG
14.3.2.2	Listing of Non-Fatal Serious Adverse Events	Safety	16.2.7.1	L_AE1_PG
14.3.2.3	Listing of Other Significant Adverse Events	Safety	16.2.7.1	L_AE1_PG
14.3.3	Narratives of deaths, other serious and significant adverse events	Safety		-
14.3.4	Summary of Laboratory Values of Potential Clinical Importance	Safety	16.2.8.1, 16.2.8.3	T_LB1
14.3.5.1	Summary of Chemistry Laboratory Values	Safety	16.4	T_LB2
14.3.5.2	Summary of Haematology Laboratory Values	Safety	16.4	T_LB2
14.3.5.3	Summary of Urinalysis Dipstick Results	Safety	16.2.8.5	T_UR1
14.3.6.1	Summary of Vital Signs	Safety	16.4	T_VS1
14.3.6.2	Summary of AUC 0-24 for Change from Baseline in Supine Diastolic Blood Pressure (h*mmHg)	Safety	16.4	T_VS2
14.3.6.3	Summary of AUC 0-24 for Change from Baseline in Supine Systolic Blood Pressure (h*mmHg)	Safety	16.4	T_VS2
14.3.6.4	Summary of AUC 0-24 for Change from Baseline in Supine	Safety	16.4	T_VS2

Table	Description	Population	Source Listing	Template (Shells below)
	Heart Rate (h*beats/min)			
14.3.7.1	Summary of ECG values	Safety	16.4	T_EG2
14.3.7.2	Summary of ECG Values and Changes in ECG Values of Potential Clinical Importance	Safety	16.4	T_EG3
14.3.8.1	Summary of Neurological Examination Data	Safety	16.2.9.5	T_NE1
14.3.8.2	Summary of Neurological Examination Questionnaire Data	Safety	16.2.9.6	T_LB2
14.3.9	Summary of Physical Examination Data	Safety	16.2.9.4	T_PE1
14.3.10	Summary of Ophthalmological Examination Data	Safety	16.2.9.7	T_NE1

CONFIDENTIAL

Figure	Description	Population	Source Listing	Template (Shells below)
14.2	PHARMACOKINETIC AND PHARMACODYNAMIC DATA			
14.2.1.1	Individual Emodepside Plasma Concentration-Time Plots (Linear and Semi-log)	PK	16.2.6.1.1	F_PK1
14.2.1.2	Geometric mean (+/- SD) Emodepside Plasma Concentration-Time Plots (Linear and Semi-log)	PK	16.2.6.1.1	F_PK2
14.2.2.1	Individual Glucose-Time Plots	PD	16.2.6.3	F_PD1
14.2.2.2	Individual Glucose and PK Concentration Plots - Including Related Significantly Important AE Durations	PD	16.2.6.3, 16.2.6.1.1, 16.2.7.1	F_PD2
14.2.3.1	Individual Insulin-Time Plots	PD	16.2.6.3	F_PD1
14.2.3.2	Individual Insulin-Time Plots 0-12h	PD	16.2.6.3	F_PD1
14.2.3.3	Individual Insulin and PK Concentration Plots - Including Related Significantly Important AE Durations	PD	16.2.6.3, 16.2.6.1.1, 16.2.7.1	F_PD2
14.2.4	Individual Glucagon-Time Plots	PD	16.2.6.3	F_PD1
14.2.5	Individual Cortisol-Time Plots	PD	16.2.6.3	F_PD1
14.3	SAFETY DATA			
14.3.1.1	Individual Systolic Blood Pressure-Time Plots	Safety	16.2.9.1	F_PD1
14.3.1.2	Individual Diastolic Blood Pressure-Time Plots	Safety	16.2.9.1	F_PD1
14.3.2	Individual Heart Rate-Time Plots	Safety	16.2.9.1	F_PD1

The following abbreviated listings will be produced (templates provided in Section 17.2.3):

Listing	Description	Template (Shells below)
16.2.1	Study dates & disposition of subjects	
16.2.1.1	Listing of Study Dates	L_SD1_PG
16.2.1.2	Listing of Reasons for Withdrawal	L_SD2_PG
16.2.2	Protocol deviations	
16.2.2.1	Listing of Subjects with Inclusion/Exclusion Criteria Deviations	L_DV1_PG
16.2.2.2	Listing of Subjects with Time Deviations	L_TD1_PG
16.2.2.3	Listing of Subjects with Other Protocol Deviations	L_DV2_PG
16.2.3	Analysis sets, including subjects excluded from analysis	
16.2.3.1	Listing of Analysis Populations	L_AN1_PG
16.2.4	Demographic data & concomitant medication	
16.2.4.1	Listing of Demographic Characteristics	L_DM1_PG
16.2.4.2	Listing of Concomitant Medications	L_CM1_PG
16.2.5	Study drug administration	
16.2.5.1	Listing of Exposure Data	L_EX1_PG
16.2.6	Pharmacokinetic and Pharmacodynamic data	
16.2.6.1.1	Listing of Emodepside Plasma Pharmacokinetic Concentration-Time Data	L_PK1_PG
16.2.6.1.2	Listing of Derived Emodepside Plasma Pharmacokinetic Parameters	L_PK4_PG
16.2.6.1.3	Individual Emodepside Plasma Concentration-Time Plots (log scale) for Estimation of $\lambda_z$ , with Regression Line	F_PK10
16.2.6.2	Listing of Emodepside Urine Excretion Rate Data	L_PK3_PG
16.2.6.3	Listing of PD concentration-Time Data	L_PK1_PG
16.2.6.4	Listing of Derived AUC0-24 PD Concentration-Time Data	L_PK1_PG
16.2.7	Adverse events	
16.2.7.1	Listing of All Adverse Events	L_AE1_PG
16.2.7.2	Listing of Serious Adverse Events	L_AE1_PG

16.2.7.3	Listing of Adverse Events Leading to Withdrawal from Study	L_AE1_PG
16.2.8	Laboratory values	
16.2.8.1	Listing of Clinical Chemistry Abnormalities of Potential Clinical Importance	L_LB1_PG
16.2.8.2	Listing of All Clinical Chemistry Laboratory Data for Subjects with PCI Abnormalities	L_LB2_PG
16.2.8.3	Listing of Haematology Abnormalities of Potential Clinical Importance	L_LB1_PG
16.2.8.4	Listing of All Haematology Laboratory Data for Subjects with PCI Abnormalities	L_LB2_PG
16.2.8.5	Listing of Urinalysis Data	L_URI
16.2.9	Vital signs, ECG variables, neurological, physical findings and Ophthalmological Assessment	
16.2.9.1	Listing of Vital Signs of Potential Clinical Importance	L_VS1_PG
16.2.9.2	Listing of ECG Values of Potential Clinical Importance	L_EG1_PG
16.2.9.3	Listing of Abnormal ECG Findings	L_EG2_PG
16.2.9.4	Listing of Abnormal Physical Examination Findings	L_PE1_PG
16.2.9.5	Listing of Neurological Examination Findings	L_NE1_PG
16.2.9.6	Listing of Neurological Questionnaire Findings	L_NE2_PG
16.2.9.7	Listing of Ophthalmological Examination Data	L_NE1_PG

Complete listings of all data collected in this study will also be produced.

